 - ^h The C-SSRS will be completed for all subjects ≥ 6 years of age.
 - ⁱ Urinalysis will be required for all subjects.
 - ^j Urine pregnancy tests will be performed for female subjects of childbearing potential only.
 - ^k Thyroid function will be required in subjects <18 years of age only.

This document cannot be used to support any marketing authorization application and any extensions or variations thereof.

REDACTED COPY

Table 5–3: Schedule of study assessments for SP0982 (Taper Period and Safety Follow-up Period)

| Assessment | Taper Period ^a (up to 4 weeks) | Safety Follow-up Period ^c | |
|--|--|---|--|
| | End of Taper Visit ^b | Safety Follow-up Visit | Safety Follow-up TC |
| | | 2 weeks (±2 days) after last dose of study drug | 30 days (-1/+3 days) after last dose of study drug |
| Concomitant medications and AED(s) | X | X | X |
| Physical exam (complete) ^k | X | X | |
| Neurological exam (complete) ^l | X | X | |
| 12-lead ECG ^h | X | X ⁱ | |
| Vital signs (BP and pulse) including orthostatic assessments ^j | X | X | |
| Body weight | X | X | |
| Laboratory tests: | | | |
| Chemistry/hematology | X | X ⁱ | |
| Endocrinology ^m | | X ⁱ | |
| Urinalysis ^f | X | X | |
| Pregnancy test ^g | X | X | |
| Contact IRT | X | | |
| Subject diary return/review ^d | X | | |
| Study drug review/return | X | | |
| Withdrawal criteria | X | | |
| AE reporting | X | X | X |
| C-SSRS ^e | X | X | |
| Healthcare resource use | X | X | |
| Work/school days lost due to epilepsy | X | X | |
| Days with help from a caregiver due to epilepsy | X | X | |
| Socio-professional data | X | X | |

AE=adverse event; AED=antiepileptic drug; BP=blood pressure; C-SSRS=Columbia-Suicide Severity Rating Scale; ECG=electrocardiogram; ET=early termination; IRT=interactive response technology; TC=telephone contact

[figure not shown]
- ^a Subjects completing Visit 10 (Week 24) or the ET Visit who choose not to continue in EP0012 must complete a blinded taper followed by the End of Taper Visit.
- ^b An End of Taper Visit will be scheduled at the end of the Taper Period (up to 4 weeks) depending on dose level achieved; see Table 7-5. Of note, for subjects who enter the Taper Period at ≤ 2 mg/kg/day (oral solution) or 100mg/day (tablets), the End of Taper Visit will take the place of the ET Visit.

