- ^c There will be a 30-day (-1/+3 days) Safety Follow-up Period for subjects who complete the End of Taper Visit. The Safety Follow-up Period consists of a clinic visit 2 weeks after the End of Taper Visit followed 2 weeks later by a TC. After the 125th event occurs, the 30-day Safety Follow up Period will be done as part of EP0012, except if the subject refuses to sign the EP0012 informed consent form. If the subject signs the informed consent form for a short Safety Follow-up as part of EP0012, the 30-day Safety Follow-up will be performed as part of EP0012; otherwise, the Safety Follow-up will be performed in SP0982.
- ^d The last subject diary will be returned at the End of Taper Visit.
- ^e The C-SSRS will be completed for all subjects ≥ 6 years of age.
- ^f Urinalysis will be required for all subjects.
- ^g Urine pregnancy tests will be performed for female subjects of childbearing potential only.
- ^h The ECG recordings should be performed at the same time of day (when possible) and prior to blood sample collection and vital sign assessments. Care should be taken to assure proper lead placement and quality ECG recordings. If possible, subjects should rest in a supine position at least 5 minutes prior to each recording and should be motionless during the recording. In pediatric subjects (<18 years of age), 12-lead ECGs (2 interpretable recordings) approximately 20 to 30 minutes apart must be performed.
- ⁱ The assessment will be required only for subjects with an abnormal value (clinical chemistry, hematology, or endocrinology) or reading (ECG) at the previous clinic visit.
- ^j Blood pressure measurements should be taken with the proper placement and proper sized cuff to obtain accurate measurements.
- ^k The complete physical examination will include cardiac and respiratory function via auscultation, and review of all body systems.
- ^l The complete neurological examination will include selected assessments of mental status, sensory systems, motor functions, cranial nerves, reflexes, and coordination/cerebellar function.
- ^m Thyroid function will be required in subjects <18 years of age only.

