8.2.3.6 Visit 10/ET Visit (end of Week 24)

Once the subject has experienced 2 PGTC seizures, the site should contact the Medical Monitor to confirm whether the subject has met the exit criteria. If the exit criteria are met, sites will be advised to have subjects return for their ET Visit within 1 week of the subject's second seizure. Once the 125th event occurs subjects will return to the site at the next scheduled visit and the ET/Visit 10 will be performed (see Section 6.3).

During the Visit 10/ET Visit (end of Week 24), the following assessments will be performed:

- Body weight
- Height
- Physical examination (complete)
- Neurological examination (complete)
- ECG 12-lead assessment (see Section 10.3.4)
- Vital signs (pulse rate, systolic BP, and diastolic BP, including orthostatic assessments)
- C-SSRS assessment (for subjects ≥ 6 years of age)
- Blood and urine samples for clinical laboratory assessments (includes hematology, chemistry, endocrinology, urinalysis, a serum pregnancy test [for women of childbearing potential], and LCM plasma concentration)
- Subject diary return/review
- Dispense subject diary
- Dispense study drug
- Study drug review/return
- Achenbach CBCL (same version used at Visit 2)
- BRIEF/ BRIEF-P (same version used at Visit 2)
- EQ-5D-3L (for subjects ≥ 12 years of age)
- QOLIE-31-P/PedsQL (same version used at Visit 2)
- Healthcare resource use
- Work/school days lost due to epilepsy

-
- Days with help from a caregiver due to epilepsy
 - Tanner Stage (will be performed only for subjects who are pubescent at Visit 2 or who enter puberty during the course of the study)
 - Socio-professional data
 - AE reporting
 - Concomitant medications and AEDs
 - Withdrawal criteria
 - Contact IRT

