8.3.1.2 Final Clinic Visit

After completing ≥ 6 weeks and experiencing the second PGTC seizure during the Treatment Period or after completing the 24-week Treatment Period or the 125th event occurs in the study (whichever comes first), eligible subjects may, at the ET Visit or Visit 10 (Week 24) respectively, choose to continue in EP0012. Subjects completing Visit 10 (Week 24) or the ET Visit must complete a 4-week blinded transition followed by a Final Clinic Visit. The Final Clinic Visit is the same as Visit 1 of EP0012. Subjects choosing to enter EP0012 must sign and date the EP0012 extension IRB/IEC-approved informed consent prior to receiving EP0012 study drug.

During the Final Clinic Visit, the following assessments will be performed:

- Body weight
- Height
- Physical examination (complete)
- Neurological examination (complete)
- ECG 12-lead assessment (see Section 10.3.1)
- Vital signs (pulse rate, systolic BP, and diastolic BP, including orthostatic assessments)
- C-SSRS assessment (for subjects ≥ 6 years of age)

-
- Blood and urine samples for clinical laboratory assessments (includes hematology, chemistry, endocrinology, urinalysis, and a urine pregnancy test [for women of childbearing potential])
 - Subject diary return/review
 - Healthcare resource use
 - Work/school days lost due to epilepsy
 - Days with help from a caregiver due to epilepsy
 - Socio-professional data
 - AE reporting
 - Concomitant medications and AEDs
 - Study drug return/review
 - Withdrawal criteria
 - Contact IRT

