8.3.2 Taper and Safety Follow-up Period

8.3.2.1 End of Taper Visit

Subjects completing Visit 10 (Week 24) or the ET Visit who choose not to continue in EP0012 must complete an up to 4-week blinded taper followed by the End of Taper Visit. At the End of Taper Visit, the following assessments will be performed:

- Body weight
- Physical examination (complete)
- Neurological examination (complete)
- ECG 12-lead assessment (see Section 10.3.1)
- Vital signs (pulse rate, systolic BP, and diastolic BP, including orthostatic assessments)
- C-SSRS assessment (for subjects ≥ 6 years of age)
- Blood and urine samples for clinical laboratory assessments (includes hematology, chemistry, urinalysis, and a urine pregnancy test [for women of childbearing potential])
- Subject diary return/review
- Study drug review/return
- Healthcare resource use
- Work/school days lost due to epilepsy
- Days with help from a caregiver due to epilepsy
- Socio-professional data
- AE reporting

- Concomitant medications and AEDs
- Withdrawal criteria
- Contact IRT

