8.3.2.2 Safety Follow-up Visit

Following the End of Taper Visit, the subject will return 2 weeks (± 2 days) after the last dose of study drug for a Safety Follow-up Visit. In case the 125th event occurs in the study, the subjects discontinuing treatment will complete a 30-day Safety Follow-up Period in the EP0012 study. The 30-day Safety Follow up Period will be done as part of EP0012, except if the subject refuses to sign the EP0012 informed consent form. If the subject signs the informed consent form for a short Safety Follow-up as part of EP0012, the 30-day Safety Follow-up will be performed as part of EP0012; otherwise, the Safety Follow-up will be performed in SP0982.

During the Safety Follow-up Visit, the following assessments will be performed:

- Body weight
- Physical examination (complete)
- Neurological examination (complete)
- ECG 12-lead assessment (see Section 10.3.1) (required only for subjects with an abnormal reading at the previous clinic visit)
- Vital signs (pulse rate, systolic BP, and diastolic BP, including orthostatic assessments)
- C-SSRS assessment (for subjects ≥ 6 years of age)
- Blood and urine samples for clinical laboratory assessments (includes hematology, chemistry, endocrinology [required only for subjects with an abnormal value at the previous clinic visit], urinalysis, and a urine pregnancy test [for women of childbearing potential]).
- Healthcare resource use
- Work/school days lost due to epilepsy
- Days with help from a caregiver due to epilepsy
- Socio-professional data
- AE reporting
- Concomitant medications and AEDs

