8.4 Unscheduled Visit

Unscheduled Visits may be performed at any time after Visit 1, as clinic visits or telephone contacts, at the discretion of the investigator. During an Unscheduled Visit, the following assessments are required:

- AE reporting
- Concomitant medications and AEDs
- Withdrawal criteria
- Contact IRT

If an Unscheduled Visit is due to an AE, then the C-SSRS (for subjects ≥ 6 years of age) is required.

In addition to the required assessments listed above, depending on the type of visit (clinic or telephone), further assessments can be completed as needed and may include ECG, vital signs, laboratory tests, dispense study drug, diary review, etc.

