10.1.3 Follow up of adverse events

An AE should be followed until it has resolved, has a stable sequelae, the investigator determines that it is no longer clinically significant, or the subject is lost to follow up. This follow-up requirement applies to AEs, SAEs, and AEs of special interest; further details regarding follow up of PDILI events are provided in Section 10.2.1.4.

If an AE is still ongoing at the end of the study for a subject, follow-up should be provided until resolution/stable level of sequelae is achieved, or until the investigator no longer deems that it is clinically significant, or until the subject is lost to follow-up. If no follow-up is provided, the investigator must provide a justification. The follow-up will usually be continued for 30 days after subjects have discontinued their IMP.

Information on SAEs obtained after clinical database lock will be captured through the PS database without limitation of time.

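### On the ordinary taper route, an abnormal thyroid value at Visit 10/ET does not by itself trigger the Safety Follow-up repeat, because the trigger points to End of Taper, where endocrinology is not scheduled

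*Protocol*

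**What the plan says.** Table 5-3 (Section 5.2) covers subjects who taper off instead of entering EP0012. Its endocrinology row is blank under End of Taper and marked under the Safety Follow-up Visit, subject to footnote i. That footnote makes the repeat "required only for subjects with an abnormal value (clinical chemistry, hematology, or endocrinology) or reading (ECG) at the previous clinic visit". Footnote m limits endocrinology to thyroid function in subjects under 18 years.

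The visit descriptions in Section 8 agree with the table:

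- Visit 10/ET (8.2.3.6) includes endocrinology: "chemistry, endocrinology, urinalysis, a serum pregnancy test [for women of childbearing potential], and LCM plasma concentration".
- End of Taper (8.3.2.1) does not: "Blood and urine samples for clinical laboratory assessments (includes hematology, chemistry, urinalysis, and a urine pregnancy test [for women of childbearing potential".
- Safety Follow-up (8.3.2.2) has it conditionally: "endocrinology [required only for subjects with an abnormal value at the previous clinic visit".

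On the other route, minors entering EP0012 have endocrinology at the Final Clinic Visit (8.3.1.2) whatever their earlier results: "chemistry, endocrinology, urinalysis, and a urine pregnancy test [for women of childbearing potential".

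Table 5-3, footnote b, adds that for subjects who start the taper at or below 2 mg/kg/day, or at 100 mg/day, "the End of Taper Visit will take the place of the ET Visit".

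**The concern.** The condition for the repeat looks back to a visit at which the test is not scheduled. Read as written, a child whose thyroid function is abnormal at the end of treatment can pass through End of Taper and Safety Follow-up without the value being rechecked, and the site would still have complied with the protocol.

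Changes in endocrinology are a listed safety variable (Section 4.2). A post-withdrawal value is what would show whether an abnormality persists once lacosamide has stopped. The last contact, by telephone at 30 days (8.3.2.3), includes no laboratory tests, so Safety Follow-up is the last scheduled opportunity on this route.

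**Working it through.** The protocol states no figure to reproduce. The check is a trace of the visit sequence, with one small piece of arithmetic on timing.

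**Sequence on the ordinary taper route** (Table 5-3, footnotes a, c and i; Sections 8.2.3.6, 8.3.2.1, 8.3.2.2)

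| Assessment | Visit 10/ET | End of Taper | Safety Follow-up | Does an abnormal result at End of Taper exist to trigger the repeat? |
|---|---|---|---|---|
| Chemistry, hematology | yes | yes | if abnormal at previous clinic visit | possible |
| 12-lead ECG | yes | yes | if abnormal at previous clinic visit | possible |
| Endocrinology (<18 years) | yes | no | if abnormal at previous clinic visit | no scheduled result |

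Footnote c places the Safety Follow-up Visit two weeks after End of Taper, with no other scheduled clinic visit between them. The previous clinic visit is therefore End of Taper, and the endocrinology condition has no scheduled thyroid result to act on. The table and the visit text agree on both the missing test and the trigger wording, so this does not come from a damaged table.

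Footnote i pools the test types. On a broad reading, an abnormal chemistry or hematology value or ECG reading at End of Taper might bring in the thyroid test. The thyroid abnormality still would not trigger its own repeat, and Section 8.3.2.2 attaches the condition directly to endocrinology.

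**Timing of the recheck, if it happened**

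Taper length follows from Table 7-5, applied to the target doses in Table 7-3:

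- 6 mg/kg/day or 300 mg/day: 2 weeks
- 7 to 8 mg/kg/day or 350 to 400 mg/day: 3 weeks
- 9 to 12 mg/kg/day: 4 weeks

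The Safety Follow-up Visit is 2 weeks (±2 days) after the last dose.

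Gap from the Visit 10/ET sample = taper length + 2 weeks = 2 + 2 to 4 + 2 = 4 to 6 weeks (±2 days).

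This assumes the Table 7-5 schedule. Section 7.2.4 also allows a slower taper if medically necessary and a faster one in an emergency.

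**Unconditional thyroid tests scheduled after Visit 10/ET:** one on the transition route (Final Clinic Visit, about 4 weeks later), none on the taper route.

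**Low-dose taper entry.** Where End of Taper replaces ET, the ET thyroid sample is not scheduled either. By the Section 8 visit lists, endocrinology appears at Visit 2 (8.2.1) and at none of Visits 3 to 9, so the last scheduled thyroid value is Visit 2. This is a related but separate gap: its cause is the visit substitution, not footnote i.

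**The case against.** The best reply is that footnote i names endocrinology as a trigger, so a sensible site would take the previous clinic visit to mean the last one with a thyroid result, namely Visit 10/ET. That reading gives every word a purpose and may well be what was intended. Neither footnote i nor Section 8.3.2.2 says it, however. The literal reading is the more natural one, and a site that followed it would omit the test and still be compliant.

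The second reply is that other provisions cover the case. Section 10.1.1.1 counts an abnormal laboratory finding among possible adverse events and requires adverse events to be recorded. Section 10.1.3 then says: "An AE should be followed until it has resolved, has a stable sequelae, the investigator determines that it is no longer clinically significant". It adds that follow-up usually runs for 30 days after the drug is stopped, which spans the Safety Follow-up Visit. Section 8.4 also provides that at an unscheduled visit "further assessments can be completed as needed and may include ECG, vital signs, laboratory tests". These provisions reduce the consequence considerably. They rest on investigator judgement, though, and do not repair the scheduled rule. What remains is mainly abnormal values that the investigator does not treat as an adverse event.

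Third, the comparison with the EP0012 route proves little by itself. Those children continue on lacosamide and the visit doubles as EP0012 Visit 1, so testing them unconditionally and tapering children conditionally is defensible. That is accepted. The finding rests on the conditional test having a condition that its own schedule does not feed.

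**Conclusion.** The point holds. On the ordinary taper route an abnormal thyroid value at Visit 10/ET does not meet the stated condition for a repeat at Safety Follow-up. The rule works for the other tests covered by footnote i and fails only for endocrinology, which points to an oversight in wording more than a deliberate choice.

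The size is not quantifiable from the protocol. The affected group is subjects under 18 years who taper, have Safety Follow-up in SP0982, and have an abnormal Visit 10/ET thyroid value not already followed as an adverse event. The recruitment target is at least 40 subjects under 18 (Section 5.1.3), and each further condition reduces that number, so the group is likely small.

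The finding does not extend to pregnancy withdrawals that go from ET to Safety Follow-up (10.1.4), or to subjects whose follow-up moves to EP0012 after the 125th event. No efficacy analysis is affected. It is a worthwhile but minor correction.

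**What to change.** 1. In Table 5-3, footnote i, make the condition: *required only for subjects with an abnormal value or reading at the last visit at which that assessment was performed (Visit 10/ET for endocrinology)*.
2. In Section 8.3.2.2, make the matching change: *endocrinology, for subjects under 18 years with an abnormal value at the last visit at which it was measured*.

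These two changes resolve the main point. They cost one footnote and one bullet, and add at most a few thyroid tests.

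For the low-dose case, add endocrinology (under 18 years) to Table 5-3 and Section 8.3.2.1 where End of Taper replaces ET.

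An alternative that covers both cases is to schedule endocrinology at End of Taper for every tapering subject under 18. That costs one thyroid test per such subject and is not needed if the trigger is reworded and the low-dose case is handled as above.

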5.3 Schematic diagrams for SP0982

The schematic diagram for the Combined Baseline Period eligibility is provided in Figure 5-1.

A schematic diagram for the Prospective Baseline Period through the Taper Period with successive panels for pediatric subjects weighing <30kg, pediatric subjects weighing ≥30kg to <50kg, and adult subjects and pediatric subjects weighing ≥50kg is provided in Figure 5-2. The schematic diagram for the Transition Period is provided in Figure 5-3.

Figure 5-1: Combined Baseline Period seizure eligibility for SP0982

This document cannot be used to support any marketing authorization application and any extensions or variations thereof.

REDACTED COPY

Figure 5-2: SP0982 Prospective Baseline Period through the Taper Period schematic diagram

[figure not shown]
[figure not shown]

Figure 5-2: SP0982 overall schematic diagram

Note: Lacosamide dosing is designated as “mg/kg/day” (oral solution) and “mg/day” (tablets) and matching placebo is shown as “placebo.”

^a Subjects will be required to achieve and maintain a minimum LCM (or matching placebo) dose for at least the final 3 days of Week 6 to be eligible for entry into the Maintenance Period.

^b If the subject discontinues from the study at any time and is not eligible or chooses not to enter EP0012, the subject must complete the ET Visit or Visit 10 (Week 24) and an up to 4-week blinded taper followed by an End of Taper Visit. There will be a 30-day Safety Follow-up Period for subjects who complete the End of Taper Visit. After the 125th event occurs, the 30-day Safety Follow up Period will be done as part of EP0012, except if the subject refuses to sign the EP0012 informed consent form. If the subject signs the informed consent form for a short Safety Follow-up as part of EP0012, the 30-day Safety Follow-up will be performed as part of EP0012; otherwise, the Safety Follow-up will be performed in SP0982.

^c If the subject is in the Titration Period when the 125th event occurs, the subject will proceed to the Transition/Taper period directly after their ET/V10 Visit.

Figure 5-3: SP0982 Transition Period schematic diagram

[figure not shown]
[figure not shown]

Figure 5-3: SP0982 Transition Period schematic diagram

Note: Lacosamide dosing is designated as “mg/kg/day” (oral solution) and “mg/day” (tablets) and matching placebo is shown as “placebo.”

^a If a subject is in the Titration Period and the next scheduled visit after the 125th event is not until Week 6, the subject will enter the Transition/Taper Period, and the escalation will be adapted accordingly.

REDACTED COPY FOR APPLICATION AND ANY EXTENSIONS OR VARIATIONS THEREOF. This document cannot be used to support any marketing authorizing application.

5.4 Rationale for study design and selection of dose

Clinical experience has shown that up to 30% of patients with PGTC seizures who are treated with currently available AEDs have insufficient seizure control or unacceptable drug tolerability. Thus, there is a significant unmet medical need for new treatment options in this patient population.

In 3 primary efficacy studies (SP667, SP754, and SP755), adjunctive LCM treatment has demonstrated efficacy and was well tolerated in the treatment of secondary generalized seizures in subjects with uncontrolled partial-onset seizures. In these studies, LCM dose titration was initiated at 100mg/day (in 2 divided doses) and escalated to the randomized dose (LCM 200mg/day, LCM 400mg/day, or LCM 600mg/day) in 100mg/day per week increments. These 3 primary efficacy studies were the basis of the approval of LCM as adjunctive therapy in the treatment of partial-onset seizures in subjects 16 years and older in the EU and 17 years and older in the US, with an established therapeutic dose range of 200mg/day to 400mg/day.

Additionally, the safety of LCM in subjects (16 to 65 years of age) with uncontrolled PGTC seizures with IGE was assessed in a clinically complete, Phase 2, multicenter, open-label, pilot study (SP0961). In this study, LCM dose titration was initiated at 100mg/day (in 2 divided doses) and increased to a maximum dose of LCM 400mg/day at weekly increments, as deemed clinically appropriate. Although evaluation of changes in PGTC seizure frequency was not intended for evaluation of efficacy, an assessment was made for exploratory purposes and a reduction in PGTC seizure frequency was observed. In addition, the AE profile was similar to that observed with adjunctive LCM for the treatment of subjects with partial-onset seizures, with the exception of seizure-related AEs.

